#### **D. Assigning study IDs for Students and SPs:**

- a. **How do we make sure we are not mixing up the numbers/giving the wrong number to a different person during the trial?**
  - i. Project staff will create a database for all participants.
  - ii. Each participant will use their student ID (their ID provided by MUHAS) number for ALL documents in the study. They will write or type in on their consent form, the baseline survey, each SP form, the post-test, and the follow-up survey, and is verbally reported on at the start of each SP videotape.
  - iii. For the electronic surveys, the programming will be set up so that the person cannot start the survey until the student ID is entered.
- b. **How do we make sure numbers are consistent for both baseline and follow-up during an intervention trial?**
  - i. Project staff are responsible, when they collect forms, to check that the student ID is on each document and that it is readable.

- ii. During data cleaning at each phase of the study, the data cleaning staff will check that the student ID number is consistent.
- c. **At the intervention:** Project staff will verify students' ID and names at the door against a master list of those randomized to the intervention before the student can enter the seminar.
- d. **At post-intervention survey.** Should pen and paper surveys be used, staff will check that there is a student ID when collecting the completed survey.
- e. **The study ID code**
  - i. Methodologist has asked for all student ID numbers to be numbers only not letters.
  - ii. The ID code for each participant is as follows:
    - a. Student ID (provided by MUHAS) followed by a hyphen, then
    - b. Profession, followed by a hyphen (with the following code), then
      - i. Medical student – 01
      - ii. Midwifery student – 02
      - iii. Nurse – 03 (Numbers correspond to the alphabetical order)
  - c. Study component number. These three digits indicate what component of the study this is:
    - i. Baseline survey – 100
    - ii. Immediate post-seminar evaluation – 200
    - iii. Follow-up survey – 300

Each SP is assigned a number from 01-12, and each study has a unique identification study number as follows:

- iv. SP Case study A – 401-412 (one for each SP) [Erectile Dysfunction ED]
- v. SP Case study B – 501-512 [Sexual violence-SV]
- vi. SP Case study C – 601-612 [Penile Drip –PD]
- vii. SP Case study D – 701-712 [ Adolescent Pregnancy]

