So, [name] is say, 09. When [name] is acting for Case Study B. the number is 509. But if [name] also works on Case study D, that would be 709.

- d. Treatment arm: [THIS INFORMATION IS DELIBERATELY NOT IN THE SOP SO THAT THE TEAM MEMBERS AT MUHAS EVALUATING THE SP VIDEOS REMAIN BLIND TO THE CODE. THE CODE IS TWO NUMBERS BETWEEN 20 AND 79 GENERATED BY METHODOLOGIST. SHE WILL SEND THESE NUMBERS TO PROJECT COORDINATOR WITH THE INSTRUCTION TO USE THEM WITH THE PARTICIPANTS AT BASELINE. AT FOLLOW-UP METHODOLOGIST WILL SEND ANOTHER SET OF NUMBERS, ALSO BETWEEN 20 AND 79 FOR USE ONLY AT FOLLOW-UP. METHODOLOGIST WILL RETAIN THE KEY TO INTERPRETING THESE DIFFERENT NUMBERS].
- e. Expert raters are assigned a number that mirrors the SPs, starting at 51-60
  - i. Expert Rater Case study A – 451-460 (one for each rater)
  - ii. Expert Rater Case study B – 551-560
  - iii. Expert Rater Case study C – 651-660
  - iv. Expert Rater Case study D – 751-760

So, **Researcher 2** is assigned a unique number, say, 55. When **Researcher 2** is evaluating Case Study B, she assigned each case 555. But if **Researcher 2** also evaluated Case Study C, she would use the number 655.

Examples:

So, the study number appearing on a survey may look like this:

671423 – 02 – 300 – 54

Student ID# – Midwifery student – follow-up survey – Intervention arm

451207 – 03 – 100 – 27

Student ID# – Nursing student – baseline survey – Control arm

671523 – 01 – 200 – 54

Student ID# – Med student – post-test survey – Intervention arm

So, the study number appearing on an SP rater form may look like this:

671523 – 01 – 401 – 54

Student ID# – Med student – Case Study A (John SP) – Intervention arm

671423 – 02 – 603 – 54

Student ID# – Midwifery student – Case Study C (Sara SP) – Intervention arm

451207 – 03 – 502 – 27

Student ID# – Nursing student – Case Study B (Mary SP) – Control arm

The number on the expert rating form will look like this

451207 – 03 – 502 – 27 – 553

Student ID# – Nurse – Case Study B (Mary SP) – Control arm – **Dr. X** rater

671423 – 02 – 402 – 54 – 455

Student ID# – Nurse – Case Study A (John SP) – Intervention arm – **Researcher 2** rater

671523 – 01 – 702 – 54 – 753

Student ID# – Nurse – Case Study D (John SP) – Intervention arm – **Dr. X** rater

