We will need 3 SPs assigned for each case and four cases, so 12 SPs in total. Assuming each SP processes 2.5 students per hour, in a 4 hour day, an SP sees 10 students. With 12 stations and each student having two cases (at baseline), that is  $20 \times 6 = 120$  students processed per day.  $120 \text{ students} \times 4 \text{ days} = 480$  students which are greater than 420 students needed for the study.

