### **4. SP Simulation Lab i.e., arrangement and setting**

This is a table from which investigators will run the simulations. The table is located in the lab.

- i. **Dr. X** is in charge of running the simulation lab.
- ii. The "control center" will be a table and several chairs located in an easily accessible location in the simulation laboratory.
- iii. All supplies and equipment will be stored/or placed in this area. All paperwork will be kept in the control center for easy access.
- iv. At least 1 staff member will always be at the control center to answer questions that students or SPs may have and to troubleshoot any problems.
- v. The control center will be maintained throughout the day and kept clean and organized.
- vi. At the end of the day during the interventions and training, all materials used for the study will be stored for the full trial use.
- vii. We have planned to have 12 simulations running concurrently in 4 rooms. Each room will have the 3 SPs with the same case. The student waits outside the room until called,

then enters the room and completes the case. When the student has completed the case they are directed to the next room to complete their second case. So, the first student completes Case A (in-room A) and then goes to Room B to complete case B. The second student goes to Room C to complete Case C and then Room D to complete Case D. The third student goes to Room A (to complete A&B), while the 4th student is sent to Room C (to complete Case C and then to Room D to complete Case D). In this way, half of the students end up completing Case A&B at baseline and half these cases at follow-up.

viii. [name] (or the person at the table) will log whether the student was assigned to cases AB or cases CD before sending them to the room. She supervises each student putting their ID number on each form.

**SP and learner's arrangement:** Each participant will complete two SP cases of about 15 minutes each, i.e., 30-40 minutes in total.

Case A: Woman who has been sexually assaulted (see **Rehema scenario**)(20 minutes)  
 Case B: Man with erectile dysfunction and homosexual history (20 minutes)  
 Case C: 16-year-old girl is worried about getting pregnant by her sugar daddy (case has been developed, see **Aliyah Scenario**) (20 minutes)  
 Case D: Young man with a drip (urethral discharge) and groin pain (case has been developed, see **Emmanuel scenario**) (20 minutes)

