#### 4. **Video Data for RCT**

A 3,296 video clips (412 participants x 4 videos x 2 admins) will each be assigned a unique code number matched to a master database. All videos are uploaded into the database and stored at two sites in Tanzania. Video data will also be saved to the BOX cloud at the end of each day.

- a. Project Coordinator is the data manager for the videos which will be saved in password-protected files. Since the videos contain identifying information (faces), he will allow access to the videos on an as necessary basis.
- b. **Rating: Drs. Y and X** will oversee the rating of videos.
- c. Videos are randomized so raters are blind to participant condition assignment (intervention or control) and blind to whether the assessment is pretest or posttest.
- d. No videos are reviewed by the expert raters until all the videos have been completed.
- e. On the rating form, the rater begins the review by writing out the Student ID, the three-digit Case-SP number (as reported on the video), and their assigned rater ID.
- f. Once the raters have rated all the videos their ratings are sent to **analyst**. **Study analyst** has the key to the blind and so can identify for each student, which are the two baseline videos and which are the two follow-up videos.

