#### 5. **Primary Dependent Variables.**

The following are the primary dependent variables:

- a. Knowledge is assessed using the 12-item knowledge quiz that is tailored to assess knowledge items taught in the curriculum.
- b. Attitude change: is from the SHEPS attitude/comfort scale
- c. Clinical skills are assessed using the clinical/expert raters review of the SP videos. See <https://link.springer.com/content/pdf/10.1023/A:1009878124073.pdf>.

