NCT03923582

R01HD092655

Title: Training for Health Professionals

Statistical Analysis Plan

Last updated: December 1, 2023

The intervention effect will be evaluated using a multiple regression analysis. The intervention group was assessed at baseline, immediately post-intervention, and follow-up, while the control group was assessed at baseline and follow-up only. Thus, difference scores (follow-up – baseline) will be calculated for each outcome listed above and used as the outcome for the regression models. "Intervention" (dummy coded as 0=control, 1=intervention) will be the primary predictor in the model. To assess whether there is a differential effect of intervention based on demographics, students' discipline, gender, and religious affiliation will be included as interaction effects (full model). In the current study, we recruited nursing, midwifery, and medical students. Due to the small number of midwifery students, midwives will be grouped with nurses for modeling purposes. Thus, discipline will be recoded into a variable called "Nursing" (0=medicine, 1=nurse/midwife). Similarly, gender will be coded as "Female" (0=male, 1=female) and religion will be coded as "Muslim" (0=Christian, 1=Muslim), based on the demographic groups with the most responses (demographic information was collected at baseline). If the interaction effects between Nursing, Female, and Muslim with Intervention are not statistically significant, the interactions will be removed from the model and the reduced model (without interaction effects but still including the main effects) will be fit and interpreted. All analyses will be run using R software (v 4.2.1).

Of the 412 recruited, one participant did not complete the post-intervention survey and three participants did not complete the three-month follow-up. Thus, these four participants will be removed from analysis. Furthermore, if participants did not identify as male/female or Christian/Muslim (e.g., responded "Other" or "Prefer Not to Answer"), they will be considered missing data and removed from analysis. Based on the demographic information collected at baseline, this will result in 396 participants for statistical modeling (96% of the total sample).

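### If the SAP's change-score rule covers clinical skills, recorded case, SP and rater differences stay in the residual: a possible loss of precision, not a bias

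*SAP*

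**What the plan says.** The protocol makes clinical skills a primary dependent variable (section I.5): "Clinical skills are assessed using the clinical/expert raters review of the SP videos". It provides identifiers for the main sources of nuisance variation. Section D numbers the actors, "Each SP is assigned a number from 01-12", and gives rater codes, "Expert raters are assigned a number that mirrors the SPs, starting at 51-60". Section F.5 sets the number of actors: "We will need 3 SPs assigned for each case and four cases, so 12 SPs in total". Under section I.4 the rater writes on the form the student ID, "the three-digit Case-SP number (as reported on the video), and their assigned rater ID".

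Section G.4 runs four rooms, one per case ("Each room will have the 3 SPs with the same case"). Students are sent alternately to the AB or the CD pair, the pair is logged, and the stated result is that half do A and B at baseline and half do them at follow-up. Section I.4 refers, for each student, to "which are the two baseline videos and which are the two follow-up videos".

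The SAP has one general rule: follow-up minus baseline differences "will be calculated for each outcome listed above and used as the outcome for the regression models". The predictors are Intervention, Nursing, Female, Muslim and their interactions with Intervention, which are dropped if not significant. Neither document has a term for case, case order, SP or rater, or a rule for combining the two ratings at a visit.

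**The concern.** A change score removes whatever is constant within a student. Here the student changes case pair between visits, and so normally changes SPs. Nothing says that the same rater scores both visits. A lenient rater, an actor who volunteers more, or an easier case can therefore raise one visit's score and not the other's. Under the SAP model all of that goes into the residual, although the labels needed to account for it are already on the forms and in the log.

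What is at stake is the width of the confidence interval for a primary outcome, the one scored by outside experts intended to be blind to arm and time point. If these sources are sizeable, the trial gives away information that it has already paid for.

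**Working it through.** **Plan's own figure.** 412 − 1 − 3 = 408. The SAP models 396, so 12 more are removed for gender or religion. 396/412 = 96.1%, which matches the stated 96%. Neither document gives a power calculation, effect size, SD or variance component, so no precision target can be reproduced.

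**Inputs from the documents.** 396 students, 1:1; 12 SPs, 3 per case; two videos per visit; AB/CD swap between visits. **Assumptions.** Single-video variance 1 (before any case-pair gap), of which a stable student share is 0.30; one rater per video; 10 raters (51-60 is a block of codes, not a stated head count); SP chosen at random within case.

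**Step 1: what is left in the change score.** With S, R and e the SP, rater and error variances, and the mean of two follow-up videos minus the mean of two baseline videos:

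Var(change) = (1/2 + 1/2)(S + R + e) = 1 − 0.30 = 0.70 if raters are assigned at random.

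The arm effect then has variance 4 × 0.70/396 = 0.0071, SE 0.084. If one rater scores all four clips, R cancels and Var(change) = S + e = 0.70 − R.

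**Step 2: best possible variance ratio, adjusted over SAP model.** Perfect adjustment leaves e = 0.70 − R − S.
- Random raters: (0.70 − R − S)/0.70.
- One rater per student: (0.70 − R − S)/(0.70 − R).

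**Step 3: achievable ratio.** Simulation of the random-effects version (variances treated as known) against the SAP model allows for estimating 12 SPs and 10 raters from finite data.

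| Rater + SP share | Random raters: bound | Random raters: simulated | One rater: bound | One rater: simulated |
|---|---|---|---|---|
| 0% + 0% | 1.00 | 1.00 | 1.00 | 1.00 |
| 5% + 2% | 0.63/0.70 = 0.90 | 0.93 | 0.63/0.65 = 0.97 | 0.98 |
| 10% + 5% | 0.55/0.70 = 0.79 | 0.83 | 0.55/0.60 = 0.92 | 0.96 |
| 20% + 5% | 0.45/0.70 = 0.64 | 0.69 | 0.45/0.50 = 0.90 | 0.91 |

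A recalculation from the generalised least squares variance formula agrees with every simulated entry to within 0.03. A ratio of 0.83 is worth 1/0.83 = 1.20 times as many students under the SAP model; 0.96 is worth 1.04 times.

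**Step 4: if the AB and CD pairs differ in difficulty.** Let the pairs sit at ±√v. The change then shifts by ±2√v according to order, adding 4v to the SAP residual.
- v = 0.05, SP + rater 10%: SAP residual 0.70 + 0.20 = 0.90. In simulation, order alone reduces the SE from 0.0954 to 0.0831, a variance ratio of 0.76. Order, SP and rater indicators together give 0.70.
- v = 0.10, SP + rater 20%: SAP residual 0.70 + 0.40 = 1.10. Order alone reduces the SE from 0.1050 to 0.0815, ratio 0.60. All indicators give 0.48.

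**Step 5: price of fixed indicators.** They add 1 (order) + 8 (two free SP contrasts in each of four cases) + 9 (raters) = 18 parameters to the SAP's 5. With no SP or rater variance the ratio is (396 − 5)/(396 − 23) = 391/373 = 1.05, and simulation also gives 1.05. Random effects give 1.00 in the same setting.

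**Step 6: bias.** Under no effect, the mean arm estimate from the SAP model lay within 0.01 of zero in every simulated setting.

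**The case against.** Several counter-arguments have force.

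- **The SAP never mentions videos, raters or clinical skills.** It refers to outcomes listed above, but no list stands in the posted text. A reader might infer that the SAP explicitly reduces clinical skills to a single raw change score. The documents do not show this. It follows only if the general rule is applied to an outcome that the protocol calls primary. The objection stands, and the point is conditional on it.
- **Rater assignment is undocumented.** A reader might infer that ten raters score clips at random, so that severity differs between a student's visits. Section I.4 randomizes videos for blinding; it does not say how clips reach raters or how many raters score each. With one rater per student most of the gain disappears. This also stands, and is why two ranges are given.
- **SPs were trained to a common portrayal** (section F) and took part in the pilot, so a small SP share is plausible. This stands. The gain could be nil.
- **The swap is stated only in the baseline section.** Section N.4 repeats the alternation without a swap rule, and section I.4 counts 3,296 clips (412 × 4 × 2) where two cases per visit give 412 × 2 × 2 = 1,648. The reading used here follows section G.4 and the reference to two videos per visit.
- **Other gains may be larger.** Under the same 0.30 student share, the correlation between visit means is 0.30/0.65 = 0.46. Using baseline as a covariate would give a ratio of (1 + 0.46)/2 = 0.73 with no rater or SP data. That is a fair point about priority, but a separate change that does not remove this one.

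**Conclusion.** The concern holds as a possible loss of precision. Case and SP differences do not cancel in a change score under the planned swap, rater severity may not, and the SAP has no term for any of them. The reduction in variance available is about 0% to 30% with randomly assigned raters and about 0% to 9% if one rater scores all of a student's clips. Both ranges cover assumed rater + SP shares of 0% to 25% and a 30% student share. Unequal case pairs would raise them.

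A reader might infer that the skills result is biased. The documents do not support that. The baseline case pair is fixed before the arm is disclosed, raters are to be blind to arm and visit, and section N calls for follow-up staff and SPs to be blind, so these factors should not differ systematically by arm. Chance imbalance is already reflected in the standard error. Nor can a large gain be taken as established, since the upper figures rest on a 20% rater share that neither document gives. The SAP analysis is valid without the change. This is a cheap improvement with an uncertain gain.

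**What to change.** For clinical skills, state in the SAP that the individual video ratings will be analysed in a linear mixed model. Fixed effects: arm, occasion, arm-by-occasion (the intervention effect), case, and the SAP's covariates. To match covariates acting on a change score, the covariates also enter by occasion. Random effects: student, rater and SP. Prefer random effects to fixed rater and SP indicators, which cost about 5% of variance if raters and SPs do not differ.

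At minimum, keep the change score and add the logged AB/CD order as a covariate.

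Also:
- Name clinical skills in the SAP's outcome list, and state how the ratings at a visit are combined wherever a change score is used.
- State how clips are assigned to raters and how many raters score each clip.
- Reconcile the case labels before using the codes. Section D has A as erectile dysfunction and B as sexual violence, and section G.4 has the reverse; C and D are also exchanged. The AB/CD pairing is unaffected.
- If outcomes have already been seen, label the model a sensitivity analysis. The SAP is dated December 2023 and already reports follow-up losses.

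Cost: a few lines of SAP text and slightly more analysis. No new data or ratings are needed.

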## C. Study Participants

**1. Inclusion criteria:** A set of standards will be used to determine which students are eligible to participate in the September 2021 randomized controlled trial (RCT):

A health student studying at MUHAS (as verified by being registered in one of the following classes):

- a. Year 2 and 3 nursing students (the final year but one or two where students have significant community and Clinical experience).
- b. Year 2 and 3 midwifery students (the final year but one or two where students have significant community and clinical experience).
- c. Year 3 and 4 medical students (the final year but one or two where students have significant community and clinical experience).
- d. Able to speak English and Swahili. Because the education seminars are in English, but history talks are in Swahili. Therefore all students must be able to understand and converse in English and Swahili.

**2. Exclusion criteria.** Students who meet the eligibility requirements above will be excluded from enrolling and participating in the RCT if::

- a. Students who will not be able to attend MUHAS on all days of the seminar
- b. If they are not available during the follow-up assessment dates.
- c. Students who express any reservations about attending (e.g., due to religious objections)
- d. Students who show fear of violence due to attending (e.g., from a spouse or relative).
- e. Students who are physically unwell during the RCT.
- f. Students who have a body temperature greater than 37.5 C.

**Procedure:** All enrollees are logged at enrollment with their name, student ID and contact details. If a student meets any of the exclusion criteria, their student ID and the reason why they were excluded will be logged.

**3. Number of participants to be enrolled for the RCT.** There will be 422 students enrolled for the September 2021 full trial: 412 of whom will be participants in the trial, plus 10 extra medical students to be waitlisted in case of absences.

- a. 284 medical students (which includes 274 confirmed participants and 10 waitlisted enrollees). Of these, 137 will be randomized to the control arm and 137 to the intervention.
- b. 103 nursing students. Of these, 52 will be randomized to the control arm and 51 to the intervention.
- c. 35 midwifery students. Of these, 18 will be randomized to the control arm and 17 to the intervention.

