## **9. Randomization of Participants to Study Arms**

**Objective:** The purpose of the randomization is to assign students to the intervention or control group arms of the trial in a way that is fair and is seen by the participants to be fair. It is also done to prevent students from trying to change their assignment from one group to the other.

We will use a block randomization for each group (midwifery, nursing and medical students), batch (in groups of ten) randomization process. Once students have completed the baseline SP and survey, they will receive their assignment in an envelope.

For logistical reasons, the students are randomized after undertaking the baseline assessment. To prevent several threats to study validity, the students and staff should not be told a student's assignment to the intervention arm or the control arm until after they have completed the baseline assessment.

- a. **Researcher 2 and Researcher 3** are in charge of the randomization.
- b. **Researcher 3** will keep three envelopes titled "midwifery", "nursing", and "medical student" envelopes. Inside these envelopes at the start of each cycle are 10 pieces of paper, all the same size. Five pieces of paper will have the word "2021" on them and five will have "2022."
- c. **Researcher 3** draws a piece of paper with 2021 on it, they will record the student who will be attending the training in 2021 (i.e., next week). If s/he draws a piece of paper with 2022 on it, they will be recording the student as eligible to attend the training in 2022.
- d. **Batch Randomization:** Once a piece of paper is drawn, it is NOT returned to the envelope but instead put in the "used envelope" for reuse later. So, when the first medical student is to be randomized, **Researcher 3** draws from the medical students' envelope with 10 pieces of paper in it; for the second, they draw from the envelope which now has 9 pieces of paper in it, and so forth. When the envelope has no more pieces of paper left in it, the envelope is refilled so it has 5 2021 and 5 2022 pieces of paper.
- e. **Researcher 3** then records the randomization on a master list of students.
- f. **Note:** Staff involved in the randomization should avoid using the terms "intervention" and "control" groups. Instead, we use the term, the training happening next week or the training for next year.

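### Discipline should enter the models' main effects as the three randomization strata; merging midwives with nurses is justified only for the interaction, though the merge costs little

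*SAP*

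**What the plan says.** Protocol section C, item 9 (Randomization of Participants to Study Arms) makes discipline the stratification factor: "We will use a block randomization for each group (midwifery, nursing and medical students), batch (in groups of ten) randomization process". Each discipline has its own envelope. "Inside these envelopes at the start of each cycle are 10 pieces of paper, all the same size", five for each training year, so allocation is 1:1 within each discipline.

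Protocol section C, item 3 gives the planned size of each stratum:
- For the 274 medical participants: "Of these, 137 will be randomized to the control arm and 137 to the intervention".
- "103 nursing students. Of these, 52 will be randomized to the control arm and 51 to the intervention".
- "35 midwifery students. Of these, 18 will be randomized to the control arm and 17 to the intervention".

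The modelling paragraph of the SAP reduces the three disciplines to two: "Due to the small number of midwifery students, midwives will be grouped with nurses for modeling purposes". The resulting variable, Nursing, is 0 for medicine and 1 for nurse or midwife. It enters the full model with its interaction with intervention, and it stays as a main effect in the reduced model if the interactions are dropped. The SAP does not say that discipline was the stratification factor, and it plans no model with the three original groups.

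**The concern.** When randomization is blocked within strata, the usual practice is to adjust for those strata, so that the reported standard error reflects the balance that the design has created. Here one stratum boundary, nurse versus midwife, is missing from every model. Nurses and midwives are forced to share one mean change score, and any true difference between them is counted as residual variation.

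The SAP's single reason, few midwives, is applied to all modelling. It fits an interaction, which needs an intervention effect estimated among midwives alone. It does not fit a main effect, which only needs a mean for that group. At stake are a little precision and a match between analysis and randomization that could be had at almost no cost.

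**Working it through.** **Inputs.** Planned counts from protocol section C, item 3 (control/intervention): medicine 137/137, nursing 52/51, midwifery 18/17. The SAP models 396 participants but gives no counts by discipline, so the planned counts are used.

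**Plan's own figure.** 274 + 103 + 35 = 412, as stated (207 control, 205 intervention). 396/412 = 96%, also as stated.

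**Step 1: does the merge bias the intervention effect?** The merged group has 103 + 35 = 138 students, 70 control and 68 intervention. Midwives are 18/70 = 25.7% of control and 17/68 = 25.0% of intervention, a difference of -0.0071. In the two-level model, each discipline group carries weight (control × intervention)/total:
- Medicine: 137 × 137/274 = 68.50.
- Merged group: 70 × 68/138 = 34.49, a share of 34.49/102.99 = 0.335.

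The shift in the intervention estimate per 1 SD midwife-nurse difference is 0.335 × (-0.0071) = -0.002 SD.

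Blocks of ten also limit how bad this can get. With 35 midwives the last block is half used, so the extreme split is 20/15. With 103 nurses it is 50/53. The share difference is then 15/68 - 20/70 = -0.065, and the shift is 0.335 × (-0.065) = -0.022 SD per 1 SD difference.

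**Step 2: what does the extra indicator cost?** In units of the residual SD, the standard error is 1/√(sum of weights):
- Two levels: 1/√(68.50 + 34.49) = 0.0985.
- Three levels: 1/√(68.50 + 52 × 51/103 + 18 × 17/35) = 1/√(68.50 + 25.75 + 8.74) = 0.0985.

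The ratio is 1.00001, so the cost is one degree of freedom.

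**Step 3: what does the merge cost?** An unmodelled midwife-nurse difference of d (in within-discipline SDs) adds this to the residual variance:

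(138/412) × (35/138) × (103/138) × d² = 0.0634 d²

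The standard error grows by the factor √(1 + 0.0634 d²). The documents give no value for d, so these are assumptions:

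| Assumed d (SD) | Added variance | Larger SE |
|---|---|---|
| 0 | 0 | none |
| 0.3 | 0.6% | 0.3% |
| 0.5 | 1.6% | 0.8% |
| 0.8 | 4.1% | 2.0% |
| 1.0 | 6.3% | 3.1% |

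**Step 4: simulation.** 10,000 trials per scenario were run with 5:5 blocks of ten in each discipline. Assumptions outside the documents: two-sided alpha 0.05, residual SD 1, and an intervention effect of 0.28 SD, chosen to give about 80% power. Gender and religion were left out.

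| d (SD) | Type I error, two vs three levels | Power, two vs three levels |
|---|---|---|
| 0 | 0.049 vs 0.050 | 80.4% vs 80.4% |
| 0.5 | 0.048 vs 0.049 | 80.6% vs 81.0% |
| 1.0 | 0.044 vs 0.050 | 78.7% vs 80.5% |

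**Step 5: where the small-number reason does hold.** The intervention effect among midwives alone has standard error √(1/18 + 1/17) = 0.34 SD, against 0.0985 SD overall. A separate midwifery interaction would be very imprecise, so merging is reasonable there.

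**The case against.** The merge is disclosed and a reason is given. It joins two groups that the protocol treats alike on entry: nursing and midwifery students both come from Years 2 and 3, and medical students from Years 3 and 4. The outcome is a change score, so stable differences in level between nurses and midwives already cancel. Gender and religion are in the model and may absorb part of whatever difference remains. The loss depends wholly on an assumed difference, and even a full SD costs under 2 points of power. All of this stands, and it is why the point is minor.

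It can also be said that 35 is a planned number. That is true, but it does not rescue the reason. The SAP removes 412 - 396 = 16 participants. If recruitment matched the plan and all 16 were midwives, 35 - 16 = 19 would remain, still enough for one indicator.

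The timing objection has more weight. The SAP is dated December 1, 2023 and already reports who missed the three-month follow-up, so a change to the main model now could look post hoc. The fix allows for this.

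A reader might infer more than the documents support:
- That the merge biases the intervention effect or inflates false positives. Blocking within each discipline prevents meaningful bias, and any error in the test is in the conservative direction.
- That the SAP ignores the stratification. It keeps the boundary between medicine and the other two disciplines and drops only the one between nurses and midwives.
- That the variance figures are the loss of precision. The loss on the standard error is about half as large.

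**Conclusion.** The mismatch is real: three randomization strata, two levels in every model, and a reason that covers the interaction but not the main effect. The analysis remains valid. Bias is about -0.002 SD per 1 SD midwife-nurse difference on planned counts. The standard error is about 0.3% to 2.0% too large for assumed differences of 0.3 to 0.8 SD, and unaffected if there is no difference.

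These figures rest on the planned 412, a common residual SD, and no adjustment for gender or religion. The point is a nearly free improvement that aligns the analysis with the randomization. It is unlikely to change a conclusion.

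**What to change.** In the full and reduced models, enter discipline as two main-effect indicators, nursing and midwifery, with medicine as reference. Keep the merged Nursing variable only in the product with intervention. It equals the sum of the two indicators, so its main effect is already in the model and it should not be added as a further main effect.

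State in the SAP that discipline was the stratification factor and that the three-level term was adopted after follow-up to match the randomization. Report the two-level model alongside, and give the analysed counts by discipline and arm.

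The cost is one degree of freedom, one extra model term, a few sentences, and one additional set of estimates.
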